8.3.11 Study procedures

The study will comprise 3 visits and 2 telephone calls.

Version: **2.0**; **08** Sep **2021** Page **34** of **61**

Visit 1 (V1) - (Day 1): Screening/Inclusion

The investigator will give oral information relative to the study to parents/legal guardians and the participant. If both parents/legal guardians agree that their child participate in the study, they will receive the information sheet and will be also asked to give a written consent. In case one parent will not be available for the visit; he/she will be asked to confirm in writing that he/she agrees with the participation of the child in the study. Children will also receive an information specific to their age and will be invited to sign an assent by the investigator.

Each screened subject will be assigned a subject identifier number during screening. The subject identifier number will contain the site number and the subject number and will be assigned in numerical order at the screening visit based on chronological order of screening dates (e.g., 01-010 for the 10th subject screened at the Site #01).

The investigator or his/her delegated designee will:

- Record demographic data and medical history and ongoing medication,
- Perform a physical and clinical examination,
- Record the score of the common cold symptoms (headache, muscle ache, chilliness, sore throat, blocked nose, runny nose, cough, sneezing according a physician-rated symptom score after clinical examination of the child; (scale: 0 3 [0: no symptom, 1 = mild symptoms (sign/symptom clearly present, but minimal awareness; easily tolerated), 2 = moderate symptoms (definite awareness of sign/symptom that is bothersome but tolerable), 3 = severe symptoms (sign/symptom that is hard to tolerate; causes interference with activities of daily living and/or sleeping]). This scoring system was developed by Jackson in 1958 and is widely used in common cold clinical trials [19],
- Verify that eligibility criteria are fulfilled,
- Record the patient choice regarding Healsea® Children use (if the patient/parents choose nasal symptoms to be treated with Healsea® Children, instructions will be given to the patient/parents for getting the test product at the end of the visit),
- Explain to the child/parents/legal guardians how to use Healsea® Children if applicable,
- Review and detail the questions of the WURSS-K,
- Explain how to use the e-diary for WURSS-K recording, how to report adverse events/

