6.4. General conventions and calculated variables**6.4.1. Subject reference start/end dates**

For each subject, the reference dates will be the following:

- The reference start date is the date of inclusion visit.
- The reference end date is the date when subject was determined to have ended the trial.

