6.4.4. Missing start/end dates of adverse events / incidents / expected side effects

In the following paragraphs, adverse events, incidents and expected side effects will be referred to as “adverse events” for ease of reading.

a) Start date

Completely missing date: it will be estimated by the reference start date.

If the day and the month are missing:

- If the year = year of reference start date, it will be estimated by the reference start date
- If the year < year of reference start date, it will be estimated by the 31st December
- If the year > year of reference start date, it will be estimated by the 1st January

If only the day is missing:

- If the month/year = month/year of reference start date, it will be estimated by the date of reference start date
- If the month/year < month/year of reference start date, it will be estimated by the last day of the month
- If the month/year > month/year of reference start date, it will be estimated by the first day of the month

If after imputation, the estimated start date is after the end date of the adverse event, it will be replaced by the end date of the adverse event.

b) End date

Note: the following rules concern events that are not “ongoing” at the end of the study.

Completely missing date: it will be estimated by the reference end date

If the day and the month are missing:

- If the year = year of reference end date, it will be estimated by the reference end date
- If the year < year of reference end date, it will be estimated by the 31st December
- If the year > year of reference end date, it will be estimated by the 1st January

If only the day is missing:

- If the month/year = month/year of reference end date, it will be estimated by the reference end date
- If the month/year < month/year of reference end date, it will be estimated by the last day of the month
- If the month/year > month/year of reference end date, it will be estimated by the first day of the month

If after imputation, the estimated end date is before the start date of the adverse event, it will be replaced by the start date of the adverse event.

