6.4.5. Missing start/end dates of concomitant medications

Same rules as for adverse events.

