8.2. Previous and concomitant medications

Previous and concomitant medications (taken at least once before reference start date) are coded by ATC class and substance name using the WHO-DRUG dictionary version 2021 Q1.

They will be summarised with frequencies and percentages.

Subjects will be counted only once within these ATC categories.

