10.3. Concomitant treatments

Concomitant treatments are coded using the WHO-DRUG dictionary version 2021 Q1.

All treatments taken at least once after reference first date or appeared during the study will be summarised by Anatomical Therapeutic Class (ATC) and substance name. The number and percentage of subjects in each category will be computed.

Subjects will be counted only once within these ATC categories. They will be analysed on the FAS.

Note: a medication which began before the reference start date and which is ongoing after the reference start date is counted in “previous medications” (see §8.2) and not in “concomitant medications”.

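### The adverse-event start-date rule, applied to medications, dates some drugs already in use at Visit 1 to Day 1 and so misplaces them in two descriptive medication tables

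*SAP*

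**What the plan says.** SAP 6.4.5 deals with missing medication dates in one line: "Same rules as for adverse events". The rules it points to are in SAP 6.4.4(a). For a start date with nothing recorded: "Completely missing date: it will be estimated by the reference start date". For a start date with only the year recorded: "If the year = year of reference start date, it will be estimated by the reference start date", but "If the year < year of reference start date, it will be estimated by the 31st December". A date lacking only the day is treated in the same way at month level: the inclusion month goes to the reference start date, and an earlier month goes to its last day. If the imputed start falls after a known end date, the end date replaces it. SAP 6.4.1 fixes the anchor: "The reference start date is the date of inclusion visit".

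Two later sections depend on the start date. SAP 8.2 defines the baseline list: "Previous and concomitant medications (taken at least once before reference start date) are coded by ATC class" and substance name. The note in SAP 10.3 says that "a medication which began before the reference start date and which is ongoing after the reference start date is counted in" the previous medications and not in the concomitant ones.

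At Visit 1 (Protocol 8.3.11) the investigator has to "Record demographic data and medical history and ongoing medication". No date rule in the SAP refers to that record.

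**The concern.** For adverse events a Day 1 default is cautious, because an event of unclear onset is then counted as treatment-emergent, as SAP 10.4 intends. For medications the same default can contradict a fact already collected: a drug noted at Visit 1 as ongoing is treated as if first taken that day.

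The population makes this plausible. Every child has a perennial sensitisation, and non-inclusion criterion 7 (Protocol 8.3.1.2) excludes only antihistamines begun less than 4 weeks earlier, so children on established antihistamines can enter. Dating such a drug to Day 1 conflicts with the child's own eligibility.

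What is at stake is the description of background therapy. Families choose the treatment (Protocol 8.2). The adjustment factors listed in SAP 10.2 are baseline temperature and baseline symptom scores; background medication is not among them. Table 14.1.2.2 is the only planned summary that sets background drugs side by side by group; beyond it there is a by-subject listing.

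**Working it through.** No figure stated in the plan depends on this rule, so there is none to reproduce. The check applies the rule literally.

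**Inputs.** Imputation: SAP 6.4.4(a) through 6.4.5. Anchor: inclusion visit (SAP 6.4.1). Classification: previous if the start is before the anchor, otherwise concomitant (SAP 8.2 and the 10.3 note). Example: a drug ongoing at Visit 1, with Visit 1 on 15 October 2021.

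| Start date recorded | Start date assigned | Before Visit 1? | Class by the 10.3 note | Correct? |
|---|---|---|---|---|
| Nothing | 15 Oct 2021 | No | Concomitant | No |
| 2021 | 15 Oct 2021 | No | Concomitant | No |
| Oct 2021 | 15 Oct 2021 | No | Concomitant | No, if begun before 15 Oct |
| Aug 2021 | 31 Aug 2021 | Yes | Previous | Yes |
| 2020 | 31 Dec 2020 | Yes | Previous | Yes |
| 2019 | 31 Dec 2019 | Yes | Previous | Yes |

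Visit 1 on 15 September 2021, 15 December 2021 or 10 January 2022 gives the same pattern. Children on the same maintenance drug can therefore be classified differently according to how precisely the start was written down.

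**Which table.** For the first three rows, Table 14.2.3 follows from the 10.3 note. Table 14.1.2.2 depends on how SAP 8.2 is read. On the imputed date the drug is lost from baseline. On the Visit 1 record it stays at baseline and, with the imputed date still governing 10.3, is counted in both tables, although the note means such a drug to be counted once.

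**How often a year-only date is affected (assumption).** Suppose true starts are spread evenly over the L months before Visit 1 and only the year is recorded. The share moved to Day 1 is the number of days from 1 January to the day before Visit 1, divided by the days in L months, with a ceiling of 100%. For Visit 1 on 15 September 2021 the numerator is 257; for 15 December 2021 it is 348.

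- L = 6: 100%
- L = 12: 257/365 to 348/365 = 70.4% to 95.3%
- L = 24: 257/730 to 348/730 = 35.2% to 47.7%
- L = 36: 257/1095 to 348/1095 = 23.5% to 31.8%

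The longer the drug has been used, the less often a year-only date is affected.

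**Effect on counts (assumption, illustration only).** With 50 background users among 100 children in a group and 10% to 40% of start dates in the affected forms, 50 × 0.10 = 5 to 50 × 0.40 = 20 users move. If the imputed date governs 8.2, the baseline table shows 45 to 30 instead of 50.

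**Direction between groups.** With 50 true users in each group and affected shares of 10% and 40%, the table shows 45 against 30: an imbalance that does not exist. With 50 and 30 true users and shares of 40% and 0%, it shows 50 × 0.60 = 30 against 30: a real imbalance hidden. Either can happen.

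**Outcome models.** SAP 10.2.4 counts use and days of use from D1 to D30. For a drug taken throughout, the count is 30 days whether the start date is in 2019, 31 December 2020 or Day 1.

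**The case against.** The strongest reply is that loss from the baseline table is not forced by the text. SAP 8.2 is worded by use before the reference date, so a drug recorded as ongoing at Visit 1 can qualify without a start date. SAP 6.4.5 is also headed for concomitant medications only. This stands in part, and it is why loss from Table 14.1.2.2 is conditional here. It does not remove the problem: the 10.3 note turns on when the drug began, the SAP nowhere says that the Visit 1 record prevails over an imputed date, and mixing the two sources counts the drug twice.

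The second reply is that little depends on it. The two tables have no between-group test in their mock layouts, and SAP 6.3.1 treats everything but the primary criterion as descriptive. Missing dates may also be few: criterion 7 obliges sites to ask when an antihistamine was started, and Protocol 10.3 provides on-line checks, queries and a clean-file review. All of this stands and limits the severity.

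A reader might infer more than the documents support:

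- That every year-only date is mishandled. It is not: an earlier year gives 31 December of that year and the drug stays at baseline.
- That baseline imbalance is understated. The direction depends on date recall in each group and is unknown.
- That the cold-medication outcome is distorted. As written, SAP 10.2.4 ignores the start date, and neither document contains a rule excluding drugs begun before Day 1 from that outcome.

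**Conclusion.** The point holds in a limited form and is minor. It concerns drugs in use at Visit 1 whose start date is completely missing, or known only to the inclusion year or the inclusion month and year. For these, the stated rule gives a Day 1 start that the Visit 1 record contradicts. They enter Table 14.2.3, and they either leave Table 14.1.2.2 or are counted in both, depending on how SAP 8.2 is read. Earlier-year and earlier-month dates are handled correctly, as are drugs with a known end date before Visit 1.

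The size cannot be stated: the documents give neither the number of background users nor a missing-date rate, and the 5 to 20 users per 100 children above rests wholly on assumption. The primary AUC analysis and the SAP 10.2.4 models are unaffected. What remains is a possible error of unknown direction in the one summary table that lets a reader compare background therapy between self-selected groups.

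**What to change.** Add to SAP 6.4.5:

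> A medication recorded at Visit 1 as ongoing, or as taken before Visit 1, whose start date is missing or incomplete and compatible with a start before the inclusion date, is dated to the latest possible day before the inclusion date and classed as previous. The adverse-event start rule applies only to medications first recorded after Visit 1.

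Keep the existing condition that an imputed start cannot be later than a known end date. For earlier-year and earlier-month dates of drugs ongoing at Visit 1, the new rule gives the same result as the present one, so only the three problem cases change.

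The cost is one addition to the SAP and one condition in the derivation program, with no new data. The downside is small: a drug truly started on Day 1 and entered as ongoing with an incomplete date would be classed as previous.

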6.4.6. AUC on total score of WURSS-K questionnaire

The computation of the AUC will be made for patients with non-missing value at D1 and at least another non-missing time point between D2 and D11. Otherwise, the AUC will be missing.

The AUC will be computed by the trapezoidal rule from D1 to D10 (Acute Phase).

If the value at D10 is missing:

- If there is no follow-up for the patient or if the value at D11 (the first day of Follow-up) is missing, then the value at D10 will be estimated by the value at the last non-missing time point before D10;
- If the value at D11 is not missing, the value at D10 will be estimated by a linear regression between the last non-missing time point before D10, noted Dj, and D11:

$$\text{WURSS}_{\text{TOT, EST}}(\text{D10}) = [\text{WURSS}_{\text{TOT}}(\text{Dj}) + (10 - j) \times \text{WURSS}_{\text{TOT}}(\text{D11})] / (11 - j)$$

7. STUDY SUBJECTS

7.1. Disposition of subjects

Screened subjects (signed informed consent) and included subjects will be summarised using frequencies and percentages as well as reasons of non-selection/non-inclusion, if applicable.

The number and percentage of subjects who withdrew prematurely after inclusion, are lost to follow-up as well as the number of completers will be described by treatment group and overall. All withdrawn subjects after their inclusion will be described regarding their main reason for withdrawal.

7.2. Protocol deviations

Protocol deviations will be discussed during the data review meeting and the status (minor or major) of these deviations will be validated in order to identify the subjects to be excluded from the Per-Protocol Set.

Major deviations are defined by:

- Non-compliance with the inclusion or exclusion criteria;
- No assessment of the primary efficacy criterion (WURSS-K) at D1, D5±1 and D10±1 during the treatment period;
- Intake of forbidden medication, i.e. nasal irrigation for patient who chose to not take Healsea® Children.

All other deviations will a priori be considered as minor, e.g.:

- Visits' dates not conform to the flow chart of the study;
- Compliance of the product Healsea® Children (see §9) not between 80% and 120%.

Major and minor deviations will be described by treatment group and overall. A listing of all deviations will be provided for all included subjects, including the type (major/minor).

7.3. Data Sets Analysed

The number and percentage of subjects in each analysis data set, as described in §5, will be provided.

8. DEMOGRAPHIC AND OTHER BASELINE CHARACTERISTICS

All demographic and baseline characteristics will be described on the FAS, by treatment group and overall.

8.1. Demographic characteristics

Age (years) and sex will be summarised using descriptive statistics already mentioned in section 6.2.

Age (years) = (reference start date – date of birth) / 365.25 (truncated at 1 digit)

8.2. Previous and concomitant medications

Previous and concomitant medications (taken at least once before reference start date) are coded by ATC class and substance name using the WHO-DRUG dictionary version 2021 Q1.

They will be summarised with frequencies and percentages.

Subjects will be counted only once within these ATC categories.

8.3. Medical and surgical past history

Medical and surgical past history is coded using the MedDRA dictionary version 20.1 and are classified by System Organ Class and Preferred Term.

The number and percentage of subjects with at least one medical and surgical past history of each category (SOC/PT) will be given.

Subjects will be counted only once within these categories.

8.4. Baseline safety variables

Symptoms of acute infectious rhinitis will be described at baseline: temperature (°C) and symptoms' scores.

For temperature and each symptoms' score, a Student (or Wilcoxon if the normality assumption is not acceptable) between-groups test will be performed.

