8.1.5 Methods and timing for assessing, recording and analysing variables

The primary endpoint will be assessed and record into an electronic diary once daily in the evening, considering the symptoms from the morning to the evening, during D1-D10. After D10, the WURSS-K will be assessed once daily until the subject feels not sick for two consecutive days. To be noted that the duration may be censored at day 30. Should the children require some or lot of help to fill in the questionnaire, this will be recorded in the diary as part of the WURSS-K questionnaire.

A specific field will be designed in the electronic diary for adverse event/incidents/expected side effects and concomitant treatments recording, contamination of relative(s) and for report of Healsea® Children intake if applicable.

> 8.1.6 Equipment to be used for assessing the clinical variables and arrangements for the monitoring maintenance and calibration

Not applicable.

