9.1 Descriptive statistics

The cohort is described: continuous variables will be summarized using the mean, standard deviation, median, minimum, maximum and quartiles, categorical variables will be summarized using frequency counts and percentages.

Two groups (called treatment groups for a sake of simplicity) will be extracted from the cohort according to the treatment chosen by the patient and a description of each group will be performed.

Details of the statistical analyses, methods and data conventions will be described in the SAP.

All statistical tests will be 2-sided and performed using a 0.05 significance level.

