4. SAMPLE SIZE

An arbitrary cohort of 200 children has been chosen. A cohort of 100-exposed and 100-not exposed patients is anticipated to allow to demonstrate the interest of using Healsea® Children in the allergic paediatric population.

Indeed, 100 patients by arms are enough to detect a Cohen's effect size of 0.4 with a power of 80% and a type I error of 5%. Cohen's effect size is defined as the standardized difference between AUC in groups. Following Cohen's methodology, 0.4 is an intermediate size between a small effect (0.2) and a medium effect (0.5) and is coherent with the expected result.

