6.3. Statistical/Analytical issues

6.3.1. Significance level

All statistical analyses will be performed at the 0.05 global significance level (type I error rate), using two-sided tests.

The statistical results are conclusive for the primary efficacy criterion.

All the other statistical results have to be considered within a descriptive perspective and not as inferential issues. No adjustment for Type I error is done. P-values of statistical tests will be provided for information only.

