10. EFFICACY

10.1. Analysis of the primary efficacy criterion

The primary objective will be analysed by performing a t-test (or a Wilcoxon test if the normality assumption is not acceptable) between the means AUC of WURSS-K score during first ten days of symptoms in each group.

The answers of the fourteen first items of the WURSS-K questionnaire are scored **from 0 to 3** (0: negative answer; from 1 to 3: positive answer with an increasing severity level). See the daily symptom report in appendix (§13.3).

The total WURSS-K score at each time point is the sum of the scores of the fourteen first items of the WURSS-K questionnaire:

$$\text{At each time point } t: \text{WURSS}_{\text{tot}}(t) = \sum_{j \in \{1, \dots, 14\}} \text{WURSS}_j(t)$$

AUC of WURSS-K score will be computed by the method described in §6.4.6.

Subjects will be analysed on the Full Analysis Set and the Per-Protocol Set.

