10.2. Analysis of the secondary efficacy criteria

The analysis of the secondary endpoints will involve multivariate analysis.

The selection of variables in multivariate analysis will be performed using a 0.20 significance level and a stepwise method. Whole the multivariate analyses specified below involve the treatment and, in order to adjust for confounding, all the potential confounding factors as explanatory variables:

- Temperature at baseline (°C);
- Symptoms' scores at baseline.

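### SAP 10.2 undertakes to adjust for all potential confounders but lists only temperature and symptom scores, so age and sex, recorded for every child, are adjusted for in no analysis

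*SAP*

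**What the plan says.** - **Allocation.** Protocol 9.1: the two groups "will be extracted from the cohort according to the treatment chosen by the patient and a description of each group will be performed". Protocol 8.1.2, on measures against bias, is marked not applicable.
- **Primary analysis.** SAP 10.1 plans "performing a t-test (or a Wilcoxon test if the normality assumption is not acceptable) between the means AUC of WURSS-K score", with no covariates. SAP 6.3.1 treats only the primary criterion as conclusive. All other results are descriptive and their p-values are for information.
- **Adjusted analyses.** SAP 10.2 says that the multivariate models include the treatment and "all the potential confounding factors as explanatory variables". The list that follows has two entries, baseline temperature and baseline symptom scores. Variables are selected stepwise at a 0.20 significance level.
- **Age and sex.** SAP 8.1: "Age (years) and sex will be summarised using descriptive statistics already mentioned in section 6.2". Mock Table 14.1.2.1 shows both by treatment group.
- **Baseline tests.** For temperature and each symptom score, SAP 8.4 states that "a Student (or Wilcoxon if the normality assumption is not acceptable) between-groups test will be performed". Mock Table 14.1.2.4 prints full summary statistics beside the p-value.
- **Who scores the outcome.** Protocol 8.1.5: "Should the children require some or lot of help to fill in the questionnaire, this will be recorded in the diary".

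**The concern.** In self-selected groups the covariate list does the work that randomisation would otherwise do. The list in SAP 10.2 is narrower than the rule it is meant to carry out, and the SAP gives no reason for leaving out age and sex.

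Age is a plausible confounder on the protocol's own facts. Children of 6 to 10 years score the outcome themselves and some are expected to need help, so scoring may vary with age. The spray is given with an adult's help and the family decides whether to use it, so uptake may vary with age too. The documents give no comparable mechanism for sex, but sex is recorded and costs almost nothing to include.

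At stake is the adjusted AUC difference, which a reader will consult to judge whether the unadjusted primary result reflects the spray or the kind of child who used it. As planned, it cannot answer that for age or sex. The SAP also sets no rule for acting on an imbalance seen in the baseline tables, so any later adjustment would be post hoc in an open-label study.

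**Working it through.** **1. The plan's own figure.** SAP 4, with the error rate set at 5%, says that "100 patients by arms are enough to detect a Cohen's effect size of 0.4 with a power of 80% and a type I error of" that level. SAP 6.3.1: "All statistical analyses will be performed at the 0.05 global significance level (type I error rate), using two-sided tests". Per group, n = 2(1.960 + 0.842)² / 0.4² = 98.1, so 99. At 100 per group the power is 80.7% by the normal approximation and 80.4% by the noncentral t with 198 degrees of freedom. The sample size reproduces, so the point concerns confounding and not arithmetic.

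**2. Which variable enters which analysis.**

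| Variable | Tabulated by group | Baseline test | Primary test | SAP 10.2 models |
|---|---|---|---|---|
| Temperature | yes | yes | no | offered, stepwise |
| Symptom scores | yes | yes | no | offered, stepwise |
| Age | yes | no | no | no |
| Sex | yes | no | no | no |

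**3. Size of what is left in the estimate.** Shift in the AUC difference (in SD of AUC) = imbalance in the covariate (in SD) × its correlation with AUC. Neither input is in the documents. Assumed: imbalance 0.1-0.3 SD, correlation 0.1-0.4.

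| Imbalance | Correlation | Shift (SD) | Share of 0.4 |
|---|---|---|---|
| 0.1 | 0.1 | 0.01 | 2.5% |
| 0.2 | 0.2 | 0.04 | 10% |
| 0.3 | 0.3 | 0.09 | 22.5% |
| 0.3 | 0.4 | 0.12 | 30% |

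For the ANCOVA, both inputs mean what remains after temperature and symptom scores. If those already carry part of the age effect, the shift is smaller. For sex, an assumed 10-point imbalance and a 0.3 SD difference in AUC between the sexes give 0.10 × 0.3 = 0.03 SD, or 7.5% of 0.4.

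**4. Cost of adding age and sex.** Power at d = 0.4, noncentral t, 100 per group:
- 198 degrees of freedom: 80.4%. With 196: 80.4%.
- If the added covariates explain a share R² of AUC variance, the effective d is 0.4/√(1 − R²). Correlations of 0.1-0.4 give R² = 0.01-0.16 and power of 80.8-86.7%.
- If age is imbalanced by 0.3 SD, its squared correlation with group is 0.3²/(0.3² + 4) = 0.022. With no gain from R², the effective d is 0.4 × √(1 − 0.022) = 0.396 and power is 79.5%.

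**5. What the baseline statistics can show.** At 100 per group, a true imbalance of 0.2 SD gives p > 0.05 with probability 71%, and one of 0.3 SD with probability 44%. A non-significant baseline test is therefore weak evidence of balance. A fixed cut-off on the standardised difference does no better. Its standard error is about √(2/100) = 0.141, so with no true imbalance its absolute value exceeds 0.1 with probability P(|Z| > 0.71) = 48%.

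**The case against.** A reader might infer that comparability is checked only by p-values, that age and sex are not compared at all, and that an imbalance in them would go unseen. The documents do not support this. SAP 8 has every demographic and baseline characteristic described by group. Table 14.1.2.1 sets age and sex side by side, Table 14.1.2.4 gives full statistics as well as p-values, and previous medication and medical history are also tabulated by group. SAP 6.3.1 makes non-primary p-values informational, and nothing in the plan says that a non-significant baseline test will be taken as balance.

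A reader might also infer that adding age and sex repairs the primary test. It does not. Shifts of 0.01-0.12 SD would put the two-sided error rate of the unadjusted t-test at 5.1-13.5%. That test is the conclusive one, and the change to SAP 10.2 leaves it as it is.

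Three further objections have force. The size rests wholly on assumed inputs, and at the low end it is negligible. Protocol 8.1.3 describes the questionnaire as designed for ages 4 to 10, which covers the enrolled range and weakens the argument that scoring depends on age, though it does not show that scores are unrelated to age. The models concerned are descriptive.

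These objections limit the point but do not remove it. Seeing an imbalance in a table does not take it out of the estimate, and SAP 10.2 still falls short of its own rule.

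**Conclusion.** The point holds, and its place is SAP 10.2. The section undertakes to adjust for all potential confounders, lists two, and lets stepwise selection drop those. Age and sex are visible by group but adjusted for nowhere, so any prognostic imbalance in them remains in the adjusted AUC difference as well as in the unadjusted one.

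The bias is conditional on age or sex being both imbalanced and related to AUC, and the documents quantify neither. Under the assumed ranges for age, the shift is 0.01-0.12 SD, about 3-30% of the effect the study was sized for. The case for acting rests less on that figure than on the low cost of meeting the rule the SAP already states. An unadjusted conclusive test in self-selected groups is a separate and larger matter that this change does not resolve.

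**What to change.** 1. SAP 10.2: add age (continuous) and sex to the listed covariates.
2. SAP 10.2.1: keep both in the AUC ANCOVA whatever their p-values, outside the stepwise selection, and show them in Tables 14.2.2.1.1 and 14.2.2.1.2.
3. Optional: print standardised differences for age, sex, temperature and the symptom scores in Tables 14.1.2.1 and 14.1.2.4. Present them as description, without a 0.1 flag.

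The data are already collected, so the cost is SAP wording, table shells and two degrees of freedom, with power at d = 0.4 staying at about 80%. The report should present this as completing the planned adjusted estimate and should not describe the primary test as corrected by it.
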